9.3.2 Cosmesis

The Breast-Q[®]’s Reconstruction Module will be tailored specifically to assess patient-reported cosmesis for patients with implant reconstructions following IMRT. With a focus on the post-operative period, the module will evaluate changes over time in four of the six subthemes identified by Breast-Q: (1) Psychosocial well-being; (2) Physical well-being; (3) Satisfaction with breasts; and (4) Satisfaction with outcome. Each subtheme will be evaluated using one or more scales. Each scale is independently scored into a value that ranges from 0 to 100, with higher score indicating greater satisfaction or better health-related quality of life. The time estimated to complete the questionnaire is 10 minutes. Additional details regarding the tailored Breast-Q are shown below:

Subtheme	Post-operative Reconstruction Module, 51 items		
	Scales/Items	Response format	Recall Period
Psychosocial well-being	Psychosocial well-being, 10 items	5-point Likert-like scales from 1 —None of the time to 5 —All of the time	In the past 2 weeks.
Physical well-being	Physical well-being, 16 items	5-point Likert-like scales from 1 —None of the time to 5 —All of the time	In the past 2 weeks.
Satisfaction with breasts	Satisfaction with breasts, 16 items; Satisfaction with breasts (implant only), 2 items	4-point Likert-like scales from 1 —Very dissatisfied to 4 —Very satisfied	In the past 2 weeks.
Satisfaction with outcome	Satisfaction with outcome, 7 items	3-point Likert-like scales from 1 —disagree to 3 —Definitely agree	None

The development phase of the Breast-Q[®] reported all scales to have Cronbach’s alphas that ranged from 0.87 to 0.98. Test-retest reliability, as measured by intraclass correlation coefficients, ranged from 0.85 to 0.98. Item response theory (Rasch) analysis was used for item reduction and scale development. In the item reduction analysis, 48% of field-test items were eliminated. Validation studies examining convergent and discriminant validity of the new measure relative to multiple existing measures (i.e. EORTC BR-23, BIS, BEQ, SF-36, PAR, BIBCQ, BSAS) are currently underway.

9.4. Assessment of Exploratory Objectives

9.4.1 Subclinical Cardiotoxicity

A subset of 20 patients with breast cancer receiving neoadjuvant chemotherapy will undergo additional assessments for evaluation of subclinical cardiotoxicity and functional performance status. These procedures are not part of routine assessments for patients receiving breast radiation and therefore will be performed on a strictly voluntary basis. All of these assessments are non-invasive and their safety and feasibility have been demonstrated in breast cancer patients who have received

chemotherapy[37]. Prior to completion of these assessments, participants will be instructed to adhere to certain fasting, substance, and activity guidelines. These guidelines are outlined in detail in Appendix 5.

9.4.2 Speckle Tracking Strain Echocardiography

From the standard 2D echocardiogram, three apical views acquired at an increased frame rate (80 frames per second) will be used for offline semi-automated speckle tracking strain analysis (Echopac, GE Medical Systems). The methods of image acquisition and strain measurements with speckle tracking have been previously described [47]. Longitudinal strain and strain rate curves will be generated for each segment, and peak global longitudinal strain will be calculated as the average value of the peak systolic strain values for all the segments within the three standard apical views. The timing of the aortic valve closure will be used to designate end-systole. A parasternal short axis view at the level of the papillary muscle will be used to obtain peak global radial and circumferential systolic strain and strain rate by averaging the peak strain value in all 6 segments of the parasternal short axis view. For strain analysis, all echocardiograms will be interpreted by a single echocardiographer blinded to whether or not patient received IMRT, 2D LVEF results, and prior strain values (study investigator: [name]). A non-sequential test ID will be assigned for each examination, identifiers and clinical information removed.

9.4.3 Cardiopulmonary Exercise Testing (CPET)

In order to determine exercise capacity, a symptom-limited cardiopulmonary exercise test to assess peak oxygen consumption ($VO_{2\text{ peak}}$) will be performed. $VO_{2\text{ peak}}$ will be evaluated using an electronic motorized treadmill test with 12-lead ECG monitoring (Mac ® 5000, GE Healthcare) performed by certified exercise physiologists.

Cardiopulmonary exercise testing is a well-established assessment of exercise capacity and provides assessment of peak oxygen consumption ($VO_{2\text{ peak}}$) [48]. Expired gases will be analyzed continuously by a metabolic measurement system (Parvo Medics, TrueOne 2400).

During the test, participants will begin walking on a treadmill at a participant-specific designated speed at 0% grade for approximately 2 minutes. The speed and/or grade will be increased every 1–2 minutes until exhaustion or a symptom-limited peak is achieved measured by peak oxygen consumption ($VO_{2\text{ peak}}$) ($\text{mL}\cdot\text{kg}^{-1}\text{min}^{-1}$).

All participants will be monitored continuously with 12-lead ECG during exercise and five minutes of recovery. During exercise, oxyhemoglobin saturation will be monitored continuously using finger pulse oximetry, while blood pressure will be measured manually by auscultatory sphygmomanometer approximately every two minutes (± 1 minute). This protocol has been previously demonstrated to be appropriate for measuring $VO_{2\text{ peak}}$ in our prior studies of early-stage and advanced cancer patients.^{22,23}

The CPET may be terminated at the discretion of the exercise physiologist if abnormal ECG findings or abnormal response to exercise is observed, or if acceptable test criteria — as outlined in Section 7.1.2.2 — are not met.

Exercise physiologists within the Cardio-Oncology Research Program (CORP) at MSKCC will perform all cardiopulmonary exercise tests. All personnel are trained to read (but not interpret) exercise ECGs and are trained in Basic Life Support (BLS) or Advanced Cardiovascular Life Support (ACLS).

The completion of the subclinical cardiotoxicity assessments will be conducted in the CORP Integrative Physiology Laboratories at Memorial Hospital, the Rockefeller Outpatient Pavilion at 53rd Street, or the Sidney Kimmel Center for Prostate and Urologic Cancers. Participants will be given an opportunity to eat a light snack following their fasted assessments. Participants will be encouraged to bring their own snack; however, the CORP team will also have extra snacks, such as granola bars, available in case participants are unable to bring their own.

9.4.4 Flow-Mediated Dilatation (FMD) via Ultrasound of the Brachial Artery

Endothelial cell dysfunction will be assessed using a commercially-available high-resolution ultrasound and a 7.5MHz linear array transducer (HP Sonos 2000). Brachial artery assessments (a surrogate of systemic nitric oxide-bioavailability) will be obtained in longitudinal view, approximately 4cm proximal to the olecranon process, in the anterior/medial plane, during the five minutes of forearm occlusion, and following cuff release (hyperemia). In patients who have received unilateral modified radical mastectomy, measurements will be performed preferably on the contralateral upper extremity. Due to the potential confounding effects, participants will be asked to adhere to fasting, substance, and activity guidelines prior to the assessment. These guidelines are defined in Appendix 5.

9.4.5 Quality of Life (QoL) and Fatigue

QOL will be assessed using the Functional Assessment of Cancer Therapy – Breast (FACT-B) scale developed for the assessment of patient symptoms and QOL in breast cancer patients. FACT is a general quality of life instrument intended for use with a variety of chronic illness conditions and was originally validated in a general cancer population that included breast cancer patients.

FACT-B is a 27-item compilation of general questions divided into four primary QOL domains: physical well-being, social/family well-being, emotional well-being, and functional well-being. This instrument has been under development since 1987 and represents the generic core questionnaire that is often combined with cancer site-specific questionnaires. FACT-B is located in Appendix 6.

FACT-B is scored by summing the individual scale scores, with higher scores indicating better quality of life. Each domain, as well as the overall QOL score is calculated according to the scoring instructions for FACT. Briefly, after reversing the scoring of negatively worded items (so that a higher score always indicated a favorable response), item responses are summed. The average value of the items for a subscale is computed for missing values, as long as >50% of the questions in the subscale were answered.

In addition to FACT-B, fatigue will be assessed using the 13-item FACIT-fatigue scale for the assessment of fatigue in cancer patients [49]. The FACIT (Functional Assessment of Chronic Illness Therapy) Measurement System has multiple disease, treatment and condition-specific subscales that will be used to complement the FACT-B questionnaire. FACIT is located in Appendix 7.

FACT-B and FACIT-fatigue QOLs will be administered post-CPET to patients in groups 2A and 2B only.

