2.3 Exploratory Objectives

- To evaluate the feasibility of performing $^{13}\text{N}-\text{NH}_3$ PET/CT scans within the radiation simulation session and correlate CFR and IMRT dose to the heart.
- To evaluate the effect of IMRT on early subclinical cardiotoxicity, as measured by speckle tracking strain echocardiography, ultrasound of the brachial artery, CPET, fatigue/quality of life questionnaires and cardiac biomarkers.
- To evaluate the effect of IMRT on fatigue and quality of life, as measured by FACT-B and FACIT questionnaires.

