3.2.2.3 Cardiopulmonary Exercise Testing/VO₂ peak Measurements

It is possible that cardiac imaging tests and flow-mediated dilatation may be unsensitive predictors of cardiotoxicity. Cardiovascular reserve, as measured by cardiopulmonary exercise testing (CPET), is considered the gold standard assessment of exercise capacity and provides assessment of peak oxygen consumption (VO₂ peak)[37]. [name] and his team have had over 10 years experience of investigating the efficacy of supervised exercise training trials in patients with cancer across the entire cancer survivorship continuum, including breast cancer patients. The information gathered by this exploratory objective will be important in understanding to what extent IMRT reduces cardiovascular reserve, and the extent to which IMRT may impact the recovery of cardiovascular reserve in the sub-acute setting after treatment.

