7.1.2.2 Group 2B

Group 2B (n=10) are patients who are receiving neoadjuvant chemotherapy and mastectomy, evaluated by Radiation Oncology for consideration of RT but do not receive RT. These 10 patients will serve as a control population against which to compare the effect of IMRT on early subclinical cardiotoxicity, and will be approached to receive the identical evaluations for assessment of cardiotoxicity as the 10 patients in the experimental group who do receive IMRT. The assessments for the control group will be performed at similar post-operative intervals as the experimental group: 4-8 weeks after surgery and at 15-20 weeks after surgery.

For breast cancer patients who receive neoadjuvant chemotherapy, it is customary for the Department of Radiation Oncology to preliminarily evaluate at a time point prior to the receipt of mastectomy. This allows adequate time for planning and sequencing of treatments, in the event that the patient opts for immediate reconstruction. After the mastectomy, the patient is seen for a second, subsequent new visit, at which time final pathology from the mastectomy is available to guide definitive treatment recommendations. We will plan to identify potential candidates for both the control and experimental arms at the first new visit prior to surgery and follow up with/enroll eligible volunteers at the second visit.

Patients in Groups 2A and 2B must meet the following inclusion criteria:

- a. Normal cardiac function (left ventricular ejection fraction $\geq 50\%$)
- b. Able to complete an acceptable baseline CPET, as determined by the absence of remarkable ECG findings or other inappropriate response to exercise
- c. Able to achieve an acceptable peak baseline CPET, as defined by any of the following criteria:

- i. achieving a plateau in oxygen consumption, concurrent with an increase in power output;
- ii. a respiratory exchange ratio ≥ 1.10 ;
- iii. attainment of maximal predicted heart rate (HR_{max}) (i.e within 10 bpm of age-predicted HR_{max} [$HR_{max}=220-Age(years)$]);
- iv. volitional exhaustion, as measured by a rating of perceived exertion (RPE) ≥ 18 on the BORG scale.

- d. Medical clearance from attending oncologist or attending radiation oncologist to undergo a symptom-limited cardiopulmonary exercise test.

Any of the following will exclude a patient from participating in Group 2A or 2B:

- a. Any of the following contraindications to cardiopulmonary exercise testing

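### Fatigue and quality-of-life forms are scheduled after a maximal exercise test with no stated interval, so acute exertion may add noise to the scores and tie them to the CPET

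*Combined protocol and SAP*

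**What the plan says.** Section 2.3 lists as an exploratory objective of its own: "To evaluate the effect of IMRT on fatigue and quality of life, as measured by FACT-B and FACIT questionnaires". Section 9.4.5 names the instruments ("fatigue will be assessed using the 13-item FACIT-fatigue scale for the assessment of fatigue in cancer patients", alongside FACT-B) and fixes their place in the sequence: "FACT-B and FACIT-fatigue QOLs will be administered post-CPET to patients in groups 2A and 2B only".

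The preceding test is described in section 9.4.3. Treadmill speed or grade is raised stepwise "until exhaustion or a symptom-limited peak is achieved measured by peak oxygen consumption". Section 7.1.2.2 lists four alternative criteria for an acceptable peak at baseline. One is volitional exhaustion, with a perceived-exertion rating of at least 18.

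The schedule tables in section 10 and the data-collection table in section 16.1 place the CPET and the questionnaires in the same windows. These are before and 2-4 weeks after radiation in Group 2A, and 4-8 and 15-20 weeks after surgery in Group 2B. No rest period, minimum interval or same-day rule between test and forms is stated.

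Section 14.1.4 compares 10 patients with IMRT and 10 without by Wilcoxon rank sum test for continuous measures, and calls the assessment preliminary. It does not say whether change from baseline or the follow-up value is compared.

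**The concern.** A fatigue scale that follows a test meant to bring the patient to her limit may record some of the tiredness the test has just caused. Two consequences would matter.

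The first is noise. How hard each patient worked and how long she rested will vary between patients and visits, and that variation would enter a comparison of 10 with 10.

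The second is loss of independence between endpoints. Section 3.2.3 treats fatigue and quality of life as possible indicators of cardiopulmonary dysfunction, and section 3.2.2.3 says the CPET is "important in understanding to what extent IMRT reduces cardiovascular reserve". If the fatigue score partly reflects the response to the CPET, agreement between the two is weaker corroboration than it appears.

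The protocol guards against this kind of influence elsewhere. Section 9.4.4 imposes activity, fasting and substance guidelines before flow-mediated dilatation because of potential confounding. Section 9.4.5 states no such control for the questionnaires and places them after the exertion.

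**Working it through.** The plan gives no effect size, standard deviation, alpha or power for fatigue or quality of life, so there is no figure to reproduce. The check is of the structure, followed by an illustration of scale.

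**1. When the order biases the comparison.** Write each observed score as the score without exercise plus a carry-over from the CPET. Let the mean carry-over at follow-up be c_A in Group 2A and c_B in Group 2B, and let Δ be the difference without carry-over.

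- Comparing follow-up values: expected difference = Δ + (c_A − c_B).
- Comparing change from baseline: expected difference = Δ + [(c_A,follow-up − c_A,baseline) − (c_B,follow-up − c_B,baseline)].

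If the carry-over is the same in both groups at each visit, the added term is zero in both lines. A constant added to every patient's score also leaves the ranks, and hence the Wilcoxon test, unchanged. Bias needs a difference between groups.

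**2. Noise when the mean carry-over is equal.** Suppose the carry-over varies between patients independently of the score, with variance v as a fraction of the score variance. The standardised effect is then multiplied by 1/√(1 + v). The range for v is an assumption; the documents give none.

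- v = 0.2: 1/√1.2 = 0.913
- v = 0.5: 1/√1.5 = 0.816

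**3. How coarse the comparison already is.** Assume two-sided alpha 0.05, 80% power, 10 per group and a normal approximation. The smallest detectable difference is (1.960 + 0.842) × √(2/10) = 2.802 × 0.447 = 1.25 SD. In a simulation of the exact Wilcoxon test (20,000 runs, normal data), power at 1.25 SD was about 70%.

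**4. What a differential carry-over would do, if there were one.** Same simulation, with no true difference and only a between-group shift from carry-over:

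| Shift (SD) | Significant results |
|---|---|
| 0 | 4.1% |
| 0.25 | 7.5% |
| 0.5 | 16.1% |
| 1.0 | 51.9% |

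These shifts are hypothetical. Nothing in the documents says which row, if any beyond the first, applies.

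**5. Does the text imply a difference between groups?** Section 3.2.2.3 contemplates that IMRT may lower cardiovascular reserve. Section 9.4.3, however, starts each patient at her own designated speed and takes her to her own limit. A patient with less reserve stops earlier; she does not perform the same absolute work. Lower reserve alone therefore does not imply more tiredness after the test. A group difference would need something further, such as slower recovery, on which the documents are silent.

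**The case against.** The strongest reply is that the order is identical in both groups and at both visits, so any common effect drops out. Step 1 confirms this, and it stands.

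A second reply is that whether exertion moves these scores depends on item wording, on recall period and on the time between test and form. Appendices 6 and 7, which hold the questionnaires, appear in the available text by title only, and that is no defect of the plan. A long recall period would lessen the problem. Section 9.4.3 also provides for a snack after the fasted assessments, so the forms need not follow straight on from testing. This stands too, and is why the point says that exertion may affect the scores.

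A reader might infer something stronger: that the forms are given at once after the treadmill, that they therefore record acute exercise fatigue, and that IMRT patients will be left more fatigued by the same test, which would bias the result against IMRT. The documents do not support this. They say only that the forms come after the CPET; they do not establish that the scores respond to it; and the test runs to each patient's own limit. Section 2.3 is worded neutrally, and section 14.1.4 states no directional hypothesis. If IMRT changed neither reserve nor recovery, this route would create no group difference.

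None of this disposes of the point. Section 9.4.5 prescribes an order; it does not leave the order open. Exertion before the form is not uniform: the peak criteria in section 7.1.2.2 are for the baseline test, and section 9.4.3 allows early termination. Stopping at one's own peak does not guarantee equal recovery.

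**Conclusion.** The concern holds as a low-severity improvement. The prescribed order lets acute exertion add noise to the fatigue and quality-of-life scores and makes them partly dependent on the CPET, which weakens them as separate evidence on IMRT.

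The size is unknown. The attenuation of 0.91 to 0.82 rests on an assumed 20% to 50% of added independent variance, and the simulated rates rest on hypothetical shifts, normal data and an assumed alpha. Bias between groups is possible but not shown. The affected comparison is voluntary, exploratory, non-randomised and 10 versus 10, and can detect only very large differences in any case. The primary endpoint, implant failure, is not affected.

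**What to change.** In section 9.4.5, replace the instruction to give FACT-B and FACIT-fatigue after the CPET with an instruction to give both forms before the CPET at the same visit, at both time points and in both groups. Carry the same order into the visit checklist.

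The visit, staff and forms stay the same. The one downside is that an acceptable baseline CPET is an inclusion criterion (section 7.1.2.2), so a few patients may complete baseline forms and then fail the test, and those forms would be discarded.

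The order should be the same at both of a patient's visits, since switching between them would itself move the change score. If the present order must stay for practical reasons, stating a minimum interval after the CPET would be a weaker substitute.

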10.0 EVALUATION DURING TREATMENT/INTERVENTION

10.1 Group 1 (IMRT to Permanent Implant)

12 months (\pm 2 months) after completion of IMRT:

- Clinical evaluations by the radiation oncologist and plastic surgeon
- Breast-Q[®] questionnaire (Appendix 4)
- Optional MRI of breast

12-18 months (\pm 6 months) after completion of IMRT:

- Follow-up ¹³N-NH₃ PET/CT
For patient subset who received cardiac ¹³N-NH₃ PET/CT during simulation

24 months (\pm 2 months) after completion of IMRT:

- Clinical evaluations by radiation oncologist and plastic surgeon
- Breast-Q[®] questionnaire (Appendix 4)
- Optional MRI of breast

10.2 Group 2 (IMRT to Tissue Expander)

12-18 months (\pm 6 months) after completion of IMRT:

- Follow-up ¹³N-NH₃ PET/CT
For patient subset who received cardiac ¹³N-NH₃ PET/CT during simulation

18 months (\pm 2 months) after completion of IMRT:

- Clinical evaluations by the radiation oncologist and plastic surgeon
- Breast-Q[®] questionnaire (Appendix 4)
- Optional MRI of breast

30 months (\pm 2 months) after completion of IMRT:

- Clinical evaluations by radiation oncologist and plastic surgeon
- Breast-Q[®] questionnaire (Appendix 4)
- Optional MRI of breast

10.2.1 Group 2A (IMRT to [Reconstructed] Breast participating in sub-study)

2-4 weeks after completion of IMRT:

- Follow-up strain echocardiogram
- CPET
- Flow-mediated dilatation (FMD)
- cardiac biomarkers for assessment of early cardiotoxicity
- FACT-B (Appendix 6) and FACIT-fatigue (Appendix 7) questionnaires for assessment of QOL and fatigue

10.2.2 Group 2B (Mastectomy and no RT participating in sub-study)

4-8 weeks post-surgery:

- Follow-up strain echocardiogram
- CPET
- Flow-mediated dilatation (FMD)
- cardiac biomarkers for assessment of early cardiotoxicity

- FACT-B (Appendix 6) and FACIT-fatigue (Appendix 7) questionnaires for assessment of QOL and fatigue

15-20 weeks post-surgery:

- Follow-up strain echocardiogram
- CPET
- Flow-mediated dilatation (FMD)
- cardiac biomarkers for assessment of early cardiotoxicity
- FACT-B (Appendix 6) and FACIT-fatigue (Appendix 7) questionnaires for assessment of QOL and fatigue

Group 1: IMRT to Permanent Implant

Protocol Activity	Screening		Treatment		Post-Treatment Follow-Up After IMRT completion		
	0-4 weeks	3-10 weeks	Day 1 _f	2-4 weeks	12 months	12-18 months	24 months
Study Week(s)/ Months	0-4 weeks	3-10 weeks	Day 1 _f	2-4 weeks	12 months	12-18 months	24 months
Visit Window	before IMRT	after exchange surgery _e	during IMRT	during IMRT	± 2mo	± 6 mo	± 2mo
Evaluation by Radiation Oncologist _a		X			X		X
Evaluation by Plastic Surgeon _a		X _b			X _c		X _c
MRI at the MSKCC main campus _d		X			X		X
BreastQ Questionnaire		X			X		X
CBC	X			X			
IMRT			X	X			
Pregnancy Test ^h	X						
¹³ N-NH ₃ PET/CT _g		X				X	

- a) Evaluation includes assessment of capsular contracture and cosmesis
- b) May occur at any time point between the exchange surgery and 10 weeks after exchange surgery.
- c) Follow-up clinical evaluations by the plastic surgeon can be from the completion of IMRT or the date of exchange surgery. This will ensure that patients are seen routinely as per standard care and will ease the schedule to accommodate changes in scheduled appointments.
- d) The MRI is an optional assessment but highly recommended
- e) This may be before IMRT or just after the start of IMRT
- f) Patients will be fully registered prior to start of Radiation Treatment (refer to section 15.0)
- g) ¹³N-NH₃ PET/CT for subset of 10 patients who agreed to participate. Baseline occurs during radiation simulation. Follow-up scan occurs 12-18 months (± 6 months) after the completion of IMRT.
- h) Pregnancy Test: Serum pregnancy is required 14 days prior to RT. A urine pregnancy test is also accepted (if performed, must be done at set-up)..

Group 2 and Group 2A: IMRT to Tissue Expander (and participating in sub-study)

Protocol Activity	Screening	Treatment		End of Treatment/ Withdrawal	Post-Treatment Follow-Up After IMRT completion			
Study Week(s)/ Months	0-4 weeks	Day 1 ^f	2-4 weeks	2-4 weeks	Approximately 4-8 months ⁱ	12-18 months	18 months	30 months
Visit Window	before IMRT	during IMRT	during IMRT	after completion of IMRT	3-10 weeks after exchange surgery	± 6mos	± 2mos	± 2mos
Evaluation by Radiation Oncologist ^a					X		X	X
Evaluation by Plastic Surgeon ^a					X _b		X _c	X _c
MRI at the MSKCC main campus ^d					X		X	X
Breast-Q [®] Questionnaire					X		X	X
CBC	X		X					
IMRT		X	X					
Pregnancy Test ⁱ	X							
¹³ N-NH ₃ PET/CT ^e	X					X		
Strain Echocardiogram ^g	X			X				
Flow-mediated dilatation (FMD)	X			X				
Cardiac Biomarkers ^g	X			X				
Cardiopulmonary Exercise Testing (CPET) ^g	X			X				
FACT-B and FACIT Questionnaires ^{g,h}	X			X				

- a) Evaluation includes assessment of capsular contracture and cosmesis
- b) May occur at any time point between the exchange surgery and 10 weeks after exchange surgery.
- c) Follow-up clinical evaluations by the plastic surgeon can be from the completion of RT or the date of exchange surgery. This will ensure that patients are seen routinely as per standard care and will ease the schedule to accommodate changes in scheduled appointments.
- d) The MRI is an optional assessment but highly recommended
- e) ¹³N-NH₃ PET/CT for subset of 10 patients who agreed to participate. Baseline occurs during radiation simulation. Follow-up scan occurs 12-18 months (± 6 months) after the completion of IMRT.
- f) Patients will be fully registered prior to start of Radiation Treatment (refer to section 15.0)
- g) **Group 2A:** In addition to the evaluations described above in Group 2, n=10 patients will undergo these evaluations for the assessment of early subclinical toxicity at these timepoints.
- h) FACT-B and FACIT questionnaires can be found in Appendices 6 and 7, respectively.
- i) The optimal time of exchange surgery will be determined by the treating plastic surgeon. The window is roughly 4-8 months after the completion of radiation therapy.
- j) Pregnancy Test: Serum pregnancy is required 14 days prior to RT. A urine pregnancy test is also accepted (if performed, must be done at set-up).

Group 2B: Mastectomy and no RT (participating in sub-study)

Protocol Activity		
Study Week(s)/ Months	4-8 weeks	15-20 weeks
Visit Window	after mastectomy	after mastectomy
Strain Echocardiogram	X	X
Flow-mediated dilatation (FMD)	X	X
Cardiac Biomarkers	X	X
Cardiopulmonary Exercise Testing (CPET)	X	X
FACT-B and FACIT Questionnaires ^a	X	X

a) FACT-B and FACIT questionnaires can be found in Appendices 6 and 7, respectively.

